ROSA Total Knee Post Market Study

A prospective, multicenter, EMEA post market clinical follow up
of the ROSA® Knee System

CME2019-24K

V3.0, 4 February 2020

STUDY SPONSOR

Zimmer GmbH Clinical Affairs

[name]

[name]

Switzerland

Study Synopsis

Title	ROSA Total Knee Post Market Study – a prospective, multi-center EMEA post market clinical follow up study for the ROSA Total knee system
Protocol Number	CME2019-24K
Sponsor	Zimmer GmbH
Manufacturer	Zimmer CAS, [name]
Study Device(s)	ROSA® Knee System
Study Objectives/Endpoints	
The main purpose of this study is to collect and compare clinical outcomes data using the commercially available ROSA Total Knee Robotic instrumentation and conventional instrumentation.
 
This will be achieved by assessing:
 
 1. Planned vs actual component positioning 2. Operative workflow efficiency 3. Patient safety based on incidence and frequency of adverse events 4. Clinical performance measured by overall pain and function, health- related quality of life data, and radiographic parameters. 
Primary endpoint: Evaluate the accuracy of implant alignment for ROSA total knee robotic instrumentation compared to conventional instrumentation, by measuring femoral rotation in the axial plane using pre op and post op CT assessments.
 
Secondary endpoints: Measure operative workflow efficiency by recording following time points during surgery: Patient in –and out time, incision – and incision closed time
 
Evaluate the change of the following scores between baseline and each post-operative follow up for performance and clinical benefits:
 
 • Oxford Knee Score • Objective Knee Assessment • Patient Satisfaction • EQ-5D • NRS Pain • FJS-12
Indications/Target population	Patients qualifying for primary total knee arthroplasty who meet the inclusion/exclusion criteria for study participation

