Inclusion/Exclusion criteria	
Inclusion criteria:
 
 • Patient is a minimum of 18 years of age • Independent of study participation, patient is a candidate for commercially available Persona, NexGen, or Vanguard knee components implanted in accordance with product labeling • Patient has participated in this study-related Informed Consent Process • Patient is willing and able to provide written Informed Consent by signing and dating the EC approved Informed Consent form • Patient is willing and able to complete scheduled study procedures and follow-up evaluations 
Exclusion criteria:
 
 • Patient is currently participating in any other surgical intervention studies or pain management studies • Patient has undergone contralateral UKA or TKA within the last 18 months • Hip pathology with significant bone loss (e.g. avascular necrosis of the femoral head with collapse, severe dysplasia of the femoral head or the acetabulum) • Hip pathology severely limiting range of motion (e.g. arthrodesis, severe contractures, chronic severe dislocation) • Patient is pregnant or considered a member of a protected population (e.g., prisoner, mentally incompetent, etc.) • Patient has previously received partial or total knee arthroplasty for the ipsilateral knee
Study Design	
Prospective, multicenter study, using Zimmer Biomet commercially available Persona, NexGen and Vanguard total knee implant system. Each consecutive, potential and eligible patient presenting as a candidate for primary knee arthroplasty will be offered study participation.
 
Selection process should be rotated on an equal basis. (eg. 5 Robotic TKA's followed by 5 Conventional TKA's and so on until enrolment is complete)

Clinical Phase	Post market
Sample Size	Maximum 8 EMEA sites, with participating surgeons contributing from 20 of each robotic and conventional knees per site. Maximum study enrolment of 240 subjects in total, including 40 subjects in the CT sub cohort
Length of Study	2,5 years (1,5 year enrolment with 1 year of follow-up). Follow-up visits at 6 weeks, 3 months and 1 year.

Materials and Methods	
Inclusion of 240 eligible subjects within maximum of 8 EMEA sites, divided into 2 groups (robotic and conventional group).
 
Sub cohort of 40 subject for CT assessment and analysis
 
Prospective follow up visit until 1 year post-operative with clinical and radiographic assessments.

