Data Collection	
Web based database (Electronic data capture system)

Statistical Reporting	
Performance will be evaluated for pain, function, health- related quality of life, and planned component position vs post-op component position. Data will be summarized descriptively additional to evaluation of data on surgical technique and instrumentation. Categorical data (e.g., gender or race) will be summarized using counts and percentages with 95% Confidence Interval (CI) limit over the time period of interest. Continuous data, such as age, will be summarized by using means, medians, SD, minimum, maximum, and 95% CI over the time period of interest. Implant survival and return to function will be summarized using a Kaplan-Meier method and presented with rates (as percentages) and CI.
 
Routine summaries of complication data is represented by frequencies and percentages. The sample size is based on a longitudinal data collection model and using functional outcomes as secondary endpoints.
 
The data from the CT sub cohort will detect for a difference in deviation from the initial alignment target proportions and presented with rates (as percentages) and CI.
 
Continuous data from pre and post-operative CT measurement will be summarized by using means, medians, SD, minimum, maximum and 95% CI over the time period of interest.

Scores/Performance Assessments	
Clinical performances are assessed by the following scores:
 
 • Oxford Knee Score • Objective Knee Assessment • Patient Satisfaction • EQ-5D • NRS Pain • FJS-12 
Radiographic performances are assessed by:
 
 • Radiographic imaging method pre- and post-operatively • Sub cohort for CT scan pre- and post-operatively
Standards	
The PMCF is compliant with the below:
 
 • The Declaration of Helsinki (DoH) - Ethical principles for medical research involving human subjects. [1] • ISO 14155: 2011 - Clinical investigation of medical devices for human subjects - Good clinical practice. [2]

References

- [1] WORLD MEDICAL ASSOCIATION DECLARATION OF HELSINKI, Ethical Principles for Medical Research Involving Human Subjects, Version October 2013.
- [2] ISO 14155:2011 International Standard for Clinical investigation of medical devices for human subjects -- Good clinical practice.

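### The primary CT comparison may rest on in-target proportions at an unstated tolerance, with no robotic-minus-conventional contrast in angular deviation specified

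*Combined protocol and SAP*

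**What the plan says.** All places are in the Study Synopsis of the combined protocol and SAP.

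- **Study Objectives/Endpoints.** The primary endpoint is comparative: "Evaluate the accuracy of implant alignment for ROSA total knee robotic instrumentation compared to conventional instrumentation". The same sentence says how accuracy will be assessed, namely "by measuring femoral rotation in the axial plane using pre op and post op CT assessments". The list of assessments includes "Planned vs actual component positioning".
- **Sample Size.** "Maximum study enrolment of 240 subjects in total, including 40 subjects in the CT sub cohort". The split of the 40 between groups is not given. For the study as a whole, the Study Design row says "Selection process should be rotated on an equal basis".
- **Statistical Reporting.** The general statement is "Data will be summarized descriptively additional to evaluation of data on surgical technique and instrumentation". Two sentences concern the CT sub cohort. The first is "The data from the CT sub cohort will detect for a difference in deviation from the initial alignment target proportions", with results given as percentages and CI. The second is "Continuous data from pre and post-operative CT measurement will be summarized by using means, medians, SD, minimum, maximum and 95% CI". The same row also lists planned against post-operative component position among the things to be evaluated.

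**The concern.** The endpoint asks which technique places the femoral component closer to plan. The analysis text does not turn that question into a defined quantity. It gives no formula for the per-knee deviation (signed or absolute), no tolerance that makes a knee in or out of target, no robotic-minus-conventional contrast in angle, and no CT split.

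The one CT sentence that speaks of a difference seems to point to proportions. Under that reading each angle becomes a yes or no at a cut-off the plan does not give. Two things are then at stake. The cut-off could be settled after the CT results are known, and it can change the result materially. In many settings the dichotomy also discards information that the same scans already supply.

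**Working it through.** **1. The plan's own figure.** The CT number is 40. It cannot be re-derived, because no alpha, power, effect, SD, outlier rate or tolerance is given for the CT endpoint. The only sample-size rationale refers to a longitudinal model and functional outcomes. There is therefore no stated figure to confirm or refute.

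**2. Assumptions for illustration.** None of these is in the documents: 20 knees per group (natural given equal rotation, but not stated), two-sided 5%, no dropout, deviations in degrees, and the SDs, biases, error shapes, cut-offs and outlier rates below.

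**3. How far the cut-off matters.** Take normal, unbiased errors with SD 2 (conventional) and SD 1 (robotic). The chance of falling outside cut-off c is 2 × (1 − Φ(c/SD)). Power is for the uncorrected chi-square test, by enumerating all 20/20 outcomes.

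| Cut-off c | Conventional outside | Robotic outside | Chi-square power |
|---|---|---|---|
| 1.5° | 2 × (1 − Φ(0.75)) = 45.3% | 2 × (1 − Φ(1.5)) = 13.4% | 64% |
| 2° | 2 × (1 − Φ(1)) = 31.7% | 2 × (1 − Φ(2)) = 4.6% | 66% |
| 3° | 2 × (1 − Φ(1.5)) = 13.4% | 2 × (1 − Φ(3)) = 0.3% | 26% |

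The knees are the same in each row; only the threshold changes.

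**4. The same knees in degrees.** The mean absolute deviation is 0.798 × SD: 1.60 degrees conventional, 0.80 robotic, a difference of 0.80. In simulation, a Welch test on absolute deviation has about 75% power, with no cut-off to choose.

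**5. Precision of a proportion difference.** The 95% half-width is 1.96 × √[(p₁q₁ + p₂q₂)/20].

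- 10% vs 0% outliers: 1.96 × √(0.09/20) = 13 points
- 20% vs 5%: 1.96 × √(0.2075/20) = 20 points
- 30% vs 10%: 1.96 × √(0.30/20) = 24 points
- 50% vs 20%: 1.96 × √(0.41/20) = 28 points

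The width depends on the assumed rates. The median Welch half-width in the normal-error simulations was 0.6 to 1.1 degrees.

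**6. Where the gain shrinks or reverses.**

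- SD 3 vs 2, normal errors, 20/20: Welch 34%, chi-square 16% to 29% over the three cut-offs.
- SD 2 vs 1 with 15 conventional and 25 robotic knees: Welch 63%, chi-square 31% to 70%.
- Very heavy tails (t with 3 df), SD 2 in both groups, conventional bias 2 degrees: Welch 62%, chi-square 71% at the 1.5-degree cut-off.

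**7. Signed or absolute.** With equal SD 2, normal errors and a pure bias of 1 or 2 degrees in one group, absolute deviation has 7% and 35% power, against 34% and 87% for the signed mean. Conversely, if the groups differ only in spread (step 3), both signed means are zero and their difference shows nothing. Neither measure is enough alone.

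**The case against.** The strongest reply is that this is a descriptive post-market study. It states no alpha, test or power, and the phrase about detecting may simply mean looking for a difference. The primary endpoint itself names the two groups and is not tied to proportions. Deviation from target is mentioned, and planned against achieved position is evaluated. Continuous CT summaries with 95% CI are planned, so if they are reported by group on the deviation, a reader could derive the difference. The advantage of degrees is also conditional, as step 6 shows.

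Most of this stands, and it limits the point. A reader might infer that 40 was miscalculated, or that the plan promises power it lacks. The documents do not support that: they claim no power for the 40. A reader might also infer that the angles are thrown away, or that proportions are certainly the primary analysis. Neither follows, since continuous summaries are planned and the key sentence is unclear.

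What the reply does not remove is that no between-group contrast is specified for a comparative primary endpoint. Summaries of pre- and post-operative measurements are not necessarily summaries of per-knee deviation from plan. The tolerance behind the proportions is still open. A descriptive study also needs to say which difference it will estimate.

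**Conclusion.** The point holds as a gap in how the primary comparison is defined, together with a better use of scans already planned. As written, the comparison may rest on dichotomised angles at a cut-off left open until after the data are seen. Under one assumed error pattern, that choice alone moves chi-square power between 26% and 66%, against about 75% for absolute deviation in degrees. These figures are illustrations under the assumptions in step 2. They do not show that degrees are always better, nor that 40 subjects are too few for a stated aim. It should be fixed, because it concerns the primary endpoint and the remedy is cheap. Confidence is medium, because the key sentence can be read in more than one way.

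**What to change.** 1. Define the per-knee deviation as planned minus post-operative femoral rotation. Make the primary analysis the robotic-minus-conventional difference in mean absolute deviation, with a 95% CI.
2. Beside it, report the signed deviation by group: the mean difference with 95% CI, and the SD in each group. This covers a pure directional bias, to which absolute deviation is insensitive.
3. Keep the in-target proportion as a secondary measure, with its tolerance in degrees fixed before the CT data are analysed.
4. Reword the CT sentence so that the sub cohort will estimate the difference between the robotic and conventional groups, and state how the 40 are split.

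A rank-based sensitivity analysis of the absolute deviation is optional, as protection against heavy tails.

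The cost is a few sentences and one derived variable, with no extra patients or scans. There are two downsides. Two deviation measures must be read together, and planned rotation must be recorded for every CT knee in both groups, including the conventional one.
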